6.10. Electrocardiogram (ECG)

A standard 12-lead ECG test will be performed to measure heart rate (min) and RR interval (msec), QRS interval (msec), PR interval (msec), QT interval (msec) and QT corrected (QTc) interval according to Fridericia's formula (msec), as well as to check for overall ECG findings, at the time points shown in Table 4.

Table 4: Time Points of 12-lead ECG in Cycle

	Time Point	Time Window
Screening Period	Any day between Day -28 and -1	
Treatment Period	Day 1: • 0 hour after the start of investigational drug administration	Before the start of infusion
	• 1 hour (at the end of infusion)	Within 60 minutes after the end of infusion
	Day 5: Cycle 1 only	
	• 0 hour after the start of investigational drug administration	Before the start of infusion
	• 1 hour (at the end of infusion)	Within 60 minutes after the end of infusion
	Day 8	± 2 days (Day 6 - 10)
Follow-up Period	Day 22	+ 7 days (Day 22 - 29)

6.11. Laboratory Tests

6.11.1. Hepatitis Virus Screening

The following hepatitis virus tests will be performed on any day during the screening period (from Day -28 to Day -1). HBV-DNA quantitative assay is not mandatory in subjects with negative results for both HBs antibody and HBc antibody.

- HCV antibody
- HBs antigen
- HBs antibody
- HBc antibody
- HBV-DNA quantification

6.11.2. Hematology, Blood Chemistry, and Blood Coagulation Tests

Hematology, blood chemistry and blood coagulation tests shown in Table 6 will be obtained at the time points shown in Table 5. Blood samples for laboratory tests should be preferably collected in the fasting state where possible, because laboratory tests include glucose measurement.

Table 5: Time Points of Blood Collection for Hematology, Blood Chemistry, and Blood Coagulation Tests in Cycle

	Time Point	Time window
Screening Period	Any day between Day -28 and -1	
Treatment Period	Day 1; before investigational drug administration	Before the start of infusion
	Day 5; after investigational drug administration: Cycle 1 only	Within 60 minutes after the end of infusion
	Day 8	± 2 days (Day 6 - 10)
	Day 15	+ 6 days (Day 15 - 21)
Follow-up Period	Day 22	+ 7 days (Day 22 - 29)

Table 6: Test Items of Hematology, Blood Chemistry, and Blood Coagulation Tests

Hematology	Hemoglobin, Hematocrit, RBC count, WBC count, WBC differential, Platelet count
Blood Chemistry	Sodium (Na), Potassium (K), Chloride (Cl), Calcium (Ca), Aspartate aminotransferase (AST), Alanine aminotransferase (ALT), Alkaline phosphatase (ALP), Lactic dehydrogenase (LDH), Total bilirubin, Total protein, Albumin, C-reactive protein (CRP), Creatinine, Blood urea nitrogen, Uric acid, Glucose
Blood Coagulation	Prothrombin time-INR (PT-INR), Prothrombin time (PT), Activated partial thromboplastin time (APTT)

6.12. Concomitant Medication/Procedures

Throughout the study period; from the day of obtaining the informed consent to the end of the follow-up period, the information listed below about concomitant medication or therapeutic procedures such as blood transfusion, wound care and oxygen inhalation will be collected.

However, the use of dilute solutions such as water for injection or saline; which are not intended for treatment; except for fluid therapy to prevent or correct problems with their fluid and/or electrolyte status, will not be determined as concomitant medication. The use of antiseptic solution, cleaning agent or heparin used for preventing blood coagulation (heparin lock) within a cannula/catheter placed in a peripheral vein; which do not have direct effect on the subject's body, will not be determined as concomitant medication. Blood transfusions should be determined as concomitant procedures.

- Medication / procedures
- Date started
- Date stopped
- Only for medication: total daily dose, unit and route
- Indication

6.13. Adverse Events

See Section 7.

6.14. Lymphoma Lesions Assessment

In this study, tumor responses will be assessed according to Revised Response Criteria for Malignant Lymphoma by an International Working Group to Standardize Response Criteria for Non-Hodgkin's Lymphomas in 2007.

Prior to the initiation of study, the PET/CT imaging devices to be used for this study will be specified, and will be used throughout the study. The same device should be used for a series of imaging tests in an individual subject. The Central Imaging Review institution will radiographically assess the PET/CT imaging devices/systems prior to the study initiation and at any change in imaging devices at each investigational site, confirm the results of phantom testing, if needed, and determine the procedures of imaging tests.

6.14.1. Baseline Assessment

The following imaging tests and examinations will be performed during the screening period (from Day -28 to Day -1) for the assessment of lymphoma lesions present at baseline:

- Radiological assessment of tumors with contrast enhanced computed tomography (contrast-enhanced CT) image data at baseline

Slice thicknesses of ≤ 5 mm will be obtained from the area covering disease lesions in the neck (infraorbital margin) to pelvis (femoral) region. Simple CT may be acceptable in a subject with known contraindication to CT contrast agents. In case that any

inadequate CT images are obtained for any reason, CT image data by Fluorodeoxyglucose-Positron Emission Tomography (FDG-PET) may be alternatively used. The detailed procedures/conditions of contrast-enhanced CT scan are specified in a separate document.

- Radiological assessment of tumors with FDG-PET data at baseline

The area covering disease lesions in the neck (infraorbital margin) to pelvis (femoral) region will be scanned. The detailed procedures/conditions of FDG-PET scan are specified in a separate document.

- Enlargement of liver or spleen (splenomegaly and hepatomegaly) will be assessed by CT scan and palpation
- Infiltration in bone marrow will be assessed by bone-marrow biopsy (biopsy should be preferred whenever possible) or aspiration (clot sections)
- For subjects with gastrointestinal lesion: lymphoid cell infiltration will be assessed by endoscopy and biopsy
- For subjects with skin lesion: photographs of skin lesion will be taken

Based on the radiological assessment at baseline, target lesions and non-target lesions will be chosen, nodal lesions or extranodal lesions will be classified, the size in 2 perpendicular dimensions of target lesions will be measured, the sum of the products of the greatest diameters (SPD) of target lesions will be calculated, and the results of FDG-PET results will be assessed.

Target and non-target lesions will be selected in consideration of reproducibility at the subsequent assessment of radiographic tumor response in the study. When nodular lesions in the liver or spleen are selected as target lesions or non-target lesions, nodular mass in the spleen will be classified as nodal lesions; and nodular mass in the liver will be classified as extranodal lesions. The enlargement of liver and spleen will be separately assessed including assessment by palpation.

<Target lesion>

- Up to 6 measurable lesions will be selected, for both enlarged lymph nodes and extranodal mass lesions. Larger lesions in order of the long diameter are preferred. See Inclusion Criteria [See Section 3.1 (5)] for the definition of measurable lesions.
- If one or more measurable lesions are found in a single lymph node region or a single organ, except for the lesion with the greatest long diameter, lesions should be selected from disparate regions of the body if possible.
- Any measurable lesions in the mediastinal or the retroperitoneal sites should be selected.

<Non-target lesion>

- All other sites of disease present at baseline and not classified as target lesions will be classified as non-target lesions, including any measurable lesions that are not chosen as target lesions.

6.14.2. Tumor Response Assessment

At the following time points, the clinical assessments and radiological assessments will be performed by the same examinations and imaging tests under the same procedures and conditions at baseline assessment, and the tumor responses will be assessed throughout the study. Any site of new lesion will be identified. Bone marrow assessment (biopsy or aspiration) will be required only if bone marrow is positive at baseline and the radiographic responses is judged to be CR.

- Any day between Day 15 and Day 21 in Cycle 3
- Any day between Day 15 and Day 21 in Cycle 6
- If administration of investigational drug is continued beyond 6 cycles, any day between Day 15 and Day 21 every 3 (\pm 1) cycles from Cycle 7
- If administration of investigational drug is discontinued at a cycle other than the above, any day between Day 15 and Day 42 in the last cycle; however, before the initiation of the subsequent treatment of primary disease

According to the response criteria defined in Table 7, the local assessment of tumor response will be performed by the principal investigator or sub-investigator.

Table 7: Revised Response Criteria for Malignant Lymphoma by an International Working Group to Standardize Response Criteria for Non-Hodgkin's Lymphomas in 2007

Response	Definition	Nodal Masses	Spleen, Liver	Bone Marrow
CR	Disappearance of all evidence of disease	(a) FDG-avid or PET positive prior to therapy; mass of any size permitted if PET negative (b) Variably FDG-avid or PET negative; regression to normal size on CT	Not palpable, nodules disappeared	Infiltrate cleared on repeat biopsy; if indeterminate by morphology, immunohistochemistry should be negative
PR	Regression of measurable disease and no new sites	\geq 50% decrease in SPD of up to 6 largest dominant masses; no increase in size of other nodes (a) FDG-avid or PET positive prior to therapy; one or more PET positive at previously involved site (b) Variably FDG-avid or PET negative; regression on CT	\geq 50% decrease in SPD of nodules (for single nodule in greatest transverse diameter); no increase in size of liver or spleen	Irrelevant if positive prior to therapy; cell type should be specified
SD	Failure to attain CR/PR or PD	(a) FDG-avid or PET positive prior to therapy; PET positive at prior sites of disease and no new sites on CT or PET (b) Variably FDG-avid or PET negative; no change in size of previous lesions on CT		
RD or PD	Any new lesion or increase by \geq 50% of previously involved sites from nadir	Appearance of a new lesion(s) $>$ 1.5 cm in any axis, \geq 50% increase in SPD of more than one node, or \geq 50% increase in longest diameter of a previously identified node $>$ 1 cm in short axis Lesions PET positive if FDG-avid lymphoma or PET positive prior to therapy	$>$ 50% increase from nadir in the SPD of any previous lesions	New or recurrent involvement

6.14.3. Radiological Assessment at the Central Imaging Review Institution

The principal investigator or sub-investigator (or designated staff) will submit imaging data by CT and FDG-PET at the following time points to the Central Imaging Review Institution. Details of the procedures of imaging data submission to the Central Imaging Review Institution are specified in a separate document.

- Screening period (between Day -28 and Day -1)

- Any day between Day 15 and Day 21 in Cycle 3
- Any day between Day 15 and Day 21 in Cycle 6
- If the administration of investigational drug is discontinued at Cycles 1, 2, 4 and 5, any day between Day 15 and Day 42 in the last cycle; however, before the initiation of the subsequent treatment of primary disease

The Central Imaging Review Institution will measure the tumor size of lymphoma lesions and evaluate FDG accumulation; according to the predefined procedure, and submit the radiological assessment results to the Efficacy and Safety Review Committee.

6.15. Survival Surveillance

6.15.1. Surveillance of Progression of Disease and Relapsed Disease

If PD, RD or “death” is not confirmed by the end of follow-up period, tumor response assessment [See Section 6.14.2] will be continued at intervals of three months or less until PD, RD or “death” is confirmed.

PD or RD includes not only the results of the radiological assessment with imaging data but also “symptomatic progression” at the principal investigator’s or sub-investigator’s judgement based on clinical symptoms or laboratory findings, etc. The development of secondary cancer is not defined as progression event, and surveillance of PD, RD or “death” will be continued.

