1.2.4. Known and Potential Risks

A total of 164 subjects received the investigational drug in 6 clinical studies conducted by ZIOPHARM. The integrated analysis includes all safety data collected and in the clinical data base as of March 31, 2012. Adverse events (AEs) occurring $\geq 5\%$ of subjects across all studies that were reported by the investigator as being at least possibly related to investigational drug include nausea (20%), fatigue (18%), dizziness (9%), anemia (8%), vomiting (8%), headache (8%), confusional state (6%), diarrhea (5%), anorexia (5%), hypomagnesemia (5%), hyperglycemia (5%), and infusion site pain (5%). Of all Grade ≥ 3 AEs that were considered possibly related to investigational drug, those occurring in ≥ 2 subjects include fatigue (4%), hyperglycemia (4%), anemia (2%), febrile neutropenia (2%), neutropenia (2%), coordination abnormal (2%), confusional state (2%), infusion site pain (1%), hypoglycemia (1%), hypokalemia (1%), hypophosphatemia (1%), mental status changes (1%), and hypoxia (1%).

In two phase 1 studies conducted by Solasia Pharma K.K. respectively in Japan and Korea in subjects with PTCL (Study SP-02L01 and SP-02L03), 23 subjects received the investigational drug. A integrated analysis of these two clinical studies indicated that investigational-drug-related AEs, occurring in ≥ 2 subjects, included constipation (17%), nausea (17%), malaise (17%), pyrexia (17%), alanine aminotransferase increased (17%), aspartate aminotransferase increased (17%), activated partial thromboplastin time prolonged (17%), decreased appetite (13%), somnolence (13%), platelet count decreased (13%), herpes zoster (9%), lymphopenia (9%), hallucination (9%), white blood cell count decreased (9%), neutrophil count decreased (9%), C-reactive protein increased (9%), and blood alkaline phosphatase increased (9%). Grade ≥ 3 investigational-drug-related AEs occurred in 4 of 23 subjects (17%), and included neutrophil count decreased (9%, 2 subjects), platelet count decreased (9%, 2 subjects), diffuse large B-cell lymphoma (4%, 1 subject), anaemia (4%, 1 subject), febrile neutropenia (4%, 1 subject), lymphopenia (4%, 1 subject), nausea (4%, 1 subject), hepatic function abnormal (4%, 1 subject), lymphocyte count decreased (4%, 1 subject), white blood cell count decreased (4%, 1 subject), and activated partial thromboplastin time prolonged (4%, 1 subject).

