2.7. Estimated Study Duration

2.7.1. Study Duration for Individual Subject

The period from the first screening visit at which the subject signs the informed consent to the day before the first day of the investigational drug administration (Day 1 of Cycle 1) is defined as a “screening period”. The period from the first day of the investigational drug administration (Day 1 of Cycle 1) to the day before the first examination, observation and investigation scheduled during the follow-up period is defined as a “treatment period”. The day on which the last (latest) examination, observation and investigation scheduled during the follow-up period is performed is defined as “the end of follow-up period”. The period from the day of the first examination, observation and investigation scheduled during the follow-up period to the end of follow-up period is defined as a “follow-up period”.

The study period consists of “a maximum of 28 days of the screening period”, “21 days of the treatment period per cycle” and “21 days of the follow-up period, in general case”. The duration of this study is estimated to be a total of 175 days; 25 weeks; approximately 6 months, when the subject is treated for 6 cycles. Additionally, the survival surveillance will be continued for up to 2 years from the first day of the investigational drug administration (Day 1 of Cycle 1).

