6.15.3. Survival Surveillance

A survival surveillance will be continued, at intervals of six months or less whenever possible, for up to 2 years from the date of initiation of investigational drug administration (Day 1 of Cycle 1) to confirm “survival” or “death” of subjects. When the subject’s death is confirmed, the “date of death” or “the most recent date (date of the last day) of survival confirmation” should be specified. The surveillance via telephone is allowed.

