7.2. Procedures for Adverse Events Reporting

The principal investigator or sub-investigator (or designated staff) will collect and identify the following information on AEs during the period from the start of investigational drug administration to the end of follow-up period, and enter a description of the event into the eCRF.

- Term of adverse event
- Date of onset
- Seriousness; serious or not serious
- Severity
- Relationship to the investigational drug; if “No,” the reason for “No”
- Any action taken; if “Yes,” the details of the action
- Outcome and date of outcome confirmation (date of resolution, date of confirmation or examination of resolving/not resolved events, date of death, etc.)

Relationship (Causality)

Relationship of an AE to the investigational drug should be assessed from the point of view that “there is a reasonable possibility that the investigational drug caused the AE”. The principal investigator or sub-investigator should determine either of “Yes” or “No”.

Severity Assessment

Severity of an AE will be assessed by the principal investigator or sub-investigator, using the 5-grade scale according to NCI-CTCAE Version 4.0. For those events not found in NCI-CTCAE Version 4.0, the principal investigator or sub-investigator will clinically determine the severity based on the definition in Table 13.

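### Phase 1 recorded a drug-related B-cell lymphoma, yet new cancers are not systematically sought or recorded once follow-up ends, for the rest of the up-to-2-year surveillance

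*Protocol*

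**What the plan says.** - **The phase 1 case.** Protocol 1.2.4 pools the two phase 1 studies in PTCL, in which "23 subjects received the investigational drug". Its list of Grade 3 or higher drug-related events includes "diffuse large B-cell lymphoma (4%, 1 subject" (of those 23).
- **Adverse event collection.** Protocol 7.2 has sites enter adverse events in the eCRF "during the period from the start of investigational drug administration to the end of follow-up period". Section 7.3 adds 4 weeks, but only for drug-related events that are already ongoing and that the investigator judges to need observation.
- **Progression surveillance.** Under Protocol 6.15.1, tumor assessment continues at intervals of three months or less until progression, relapse or death. On new cancers it states: "The development of secondary cancer is not defined as progression event". Surveillance then carries on, and no instruction to record the cancer follows.
- **Other surveillance data.** Section 6.15.2 collects later treatment for the primary disease. Section 6.15.3 reads: "A survival surveillance will be continued, at intervals of six months or less whenever possible, for up to 2 years". It asks for vital status and dates, allows contact by telephone, and does not ask for cause of death.
- **SAE reporting.** Protocol 7.4 requires any SAE to be reported within 24 hours of the site knowing of it and gives no end date.
- **SAP.** Section 12.1 and the listings in section 13 contain no second-malignancy output. The events of special interest in 12.1.6 are psychiatric, nervous system and hepatobiliary disorders.

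**The concern.** A B-cell lymphoma reported as an adverse event in subjects with T-cell lymphoma is reasonably read as a new malignancy, and the investigator attributed it to the drug. The protocol expects that such cancers may occur during surveillance, because it has to say how they count for progression. It then gives no rule for capturing them.

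At stake is how completely an event already linked to the drug is ascertained. Sites will be in touch with surviving subjects for up to 2 years, but the planned questions cover only progression, treatment of the lymphoma, and whether the subject is alive. A non-fatal new cancer after follow-up would reach the database only if a site chose to report it. A fatal one could appear simply as a date of death. The primary endpoint, sample size and error rates are not affected.

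**Working it through.** **Inputs.** Protocol 2.7.1 gives "a maximum of 28 days of the screening period", "21 days of the treatment period per cycle" and 21 days of follow-up in the general case. It also gives a total of 175 days for six cycles and surveillance for up to 2 years (taken as 730 days) from Day 1 of Cycle 1. The follow-up visit is at Day 22 of the last cycle (Tables 2 to 5).

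**Step 1: reproduce the plan's figure.** 28 + 6 × 21 + 21 = 175 days, or 25 weeks. This matches, so the period lengths are read correctly.

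**Step 2: length of adverse event collection from first dose.**
- Shortest, ending at the Day 22 visit: (cycles − 1) × 21 + 22. For six cycles this is 5 × 21 + 22 = 127 days.
- General case, with 21 days of follow-up: cycles × 21 + 21. For six cycles this is 6 × 21 + 21 = 147 days.

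**Step 3: days not covered, for a subject who survives 2 years.** Uncovered share = (730 − window) / 730.

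| Scenario | Window (days) | Uncovered days | Share |
|---|---|---|---|
| 3 cycles, general case | 84 | 646 | 88.5% |
| 6 cycles, shortest | 127 | 603 | 82.6% |
| 6 cycles, general case | 147 | 583 | 79.9% |
| 6 cycles, plus 4 weeks as if section 7.3 caught new events | 175 | 555 | 76.0% |
| 6 cycles, +7 days at each of 5 intervals | 182 | 548 | 75.1% |
| 6 cycles, 3-week postponement at each of 5 intervals, plus 4 weeks | 280 | 450 | 61.6% |
| 12 cycles | 273 | 457 | 62.6% |
| 16 cycles | 357 | 373 | 51.1% |
| 17 cycles | 378 | 352 | 48.2% |

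More than half of the 2 years is uncovered for on-schedule treatment of up to 16 cycles.

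**Step 4: allow for deaths.** The documents give no survival figure, so exponential survival is assumed. With a hazard of ln 2 / median, the person-time uncovered is 1 − [1 − exp(−hazard × 147)] / [1 − exp(−hazard × 730)].
- Median 12 months (365 days): 1 − 0.244 / 0.750 = about 68%.
- Median 6 months (182.5 days): 1 − 0.428 / 0.9375 = about 54%.

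**Step 5: size of the phase 1 signal.** 1/23 = 4.3%. The Clopper-Pearson 95% limits are the 2.5% point of Beta(1, 23) and the 97.5% point of Beta(2, 22), which give 0.1% and 21.9%. If the same rate applied to 65 subjects (an assumption), 65 × 1/23 = 2.8 cases would be expected, with a range of 0.07 to 14.3 from the interval limits.

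**The case against.** **Section 7.4 may already reach these events.** It requires any SAE to be reported once the site knows of it and sets no end date. Most new cancers would plausibly meet a criterion in 7.1.2. Before progression, an investigator who separates a new cancer from progression at a three-monthly assessment does know of it. This stands in part. A reader might infer that a cancer after follow-up is recorded nowhere, but the documents do not support that. What they leave is an unresolved tension between 7.2, which is bounded, and 7.4, which is not. No question prompts a report, and the tumor assessments stop at progression.

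**Contact is not guaranteed.** A reader might infer that every subject is contacted for 2 years. Section 6.15.3 says up to 2 years and whenever possible, so deaths and losses end contact.

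**The uncovered share is not a share of missed cancers.** It is tempting to say that 80% to 91% of new cancers would be missed (91% being a three-cycle subject on the shortest window), or that such cancers typically appear late. The first needs uniform onset, survival to 2 years and no extended treatment. The documents support none of these and give no onset time for the phase 1 case.

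**The signal is thin and the count would be hard to interpret.** There is one attributed case. The protocol does not call it a second primary, and it was captured as an adverse event in phase 1. The present trial has no control arm, and its subjects have had prior antitumor therapy and may receive more. All of this stands. It limits what the count can show, but it is not a reason to leave ascertainment to chance.

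**The sentence on secondary cancer is a progression rule.** That is correct, and the sentence is not itself at fault. The gap is that no companion safety rule exists.

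**Conclusion.** The concern holds as a gap in active collection. After the end of follow-up, new malignancies are neither systematically sought nor recorded, although one was attributed to the drug in phase 1 and section 6.15.1 foresees them. For a six-cycle subject on schedule who survives 2 years, 583 to 603 of 730 days (80% to 83%) are uncovered. Under the assumed medians of 12 and 6 months, about 68% and 54% of person-time is uncovered with a 147-day window. Delays and extended treatment lower the share further, to under half at 17 or more cycles.

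These figures describe time covered. They say nothing about how many cancers would occur or be lost, and the phase 1 rate is too imprecise to predict that. The change is worth making because it is cheap and improves the safety data captured.

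**What to change.** 1. **Protocol 6.15.3:** at each surveillance contact already planned, ask about and record any new malignancy, with type, date of diagnosis and the investigator's causality assessment.
2. **Protocol 7.2 and 7.4:** reconcile the two by stating the period over which second malignancies are reported as SAEs.
3. **SAP 12.1 and 13:** add a count and a listing of second malignancies over surveillance. Show time since first dose and any subsequent therapy, which section 6.15.2 already collects.

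**Cost.** One question at existing contacts, one eCRF item, and one SAP count and listing, with no new visit or procedure. It still needs an amendment in four countries/regions to a protocol at version 3.5 (January 2020) whose surveillance is planned to end in December 2021, so the gain depends on how many subjects remain in contact. Telephone contact will limit diagnostic and causality detail. The count will be small, uncontrolled and confounded by prior and subsequent therapy, and should be presented as descriptive.
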